  - Subjects who received prior CD19-targeting treatment are allowed (CAR-T cell therapy is excluded) A biopsy following CD19-targeting treatment is required unless no lesions are accessible or the risk of the biopsy is deemed too high by the investigator
- 105. For DLBCL: Refractory (no prior **CR**/CMR) to first or later line of treatment or relapsed (prior CR/CMR) after two or more prior treatments, with at least one treatment consisting of standard multiagent chemotherapy containing an anthracycline AND an approved anti-CD20 agent. Examples of appropriate therapy include but are not limited to R-CHOP (14 or 21), R-CHOEP, and DA-R-EOCH.

For FL: Refractory (no prior CR/CMR) to first or later line of treatment or relapsed (prior CR/CMR) after three or more prior treatments, with at least one treatment consisting of a standard chemotherapy containing an approved anti-CD20 agent. Examples of appropriate therapy include but are not limited to R-CHOP, R-CVP, and BR.

For MCL: Refractory (no prior CR/CMR) to first or later line of treatment or relapsed (prior CR/CMR) after three or more prior treatments, with at least one treatment consisting of a standard chemotherapy containing an approved anti-CD20 agent. Examples of appropriate therapy include but are not limited to R-CHOP, BR and hyper-CVAD alternating with R-MTX/Ara-C.

For subjects with refractory B-NHL and who have received radiotherapy, PET positivity should be demonstrated no less than 6 weeks after the last dose of radiotherapy

106. Minimum life expectancy of 12 weeks

- 107. Radiographically measurable disease with a clearly demarcated nodal lesion at least 1.5 cm in its largest dimension or a target extranodal lesion at least 1.0 cm in its largest dimension. In the dose exploration phase in case disease is not radiographically measurable PET positivity (ie, Deauville ≥4) instead is acceptable.
- 108. Eastern Cooperative Oncology Group (ECOG) performance status  $\leq 2$
- 109. Laboratory parameters (completed within 14 days prior to enrollment): Hematology:
  - Absolute neutrophil count (ANC) ≥ 1.0 x 10^9/L
  - Platelets  $\geq$  75 x 10^9/L

Chemistry:

- Creatinine clearance ≥ 60 mL/min (calculated **using Cockcroft Gault** equation)
- Aspartate aminotransferase (AST)/alanine aminotransferase (ALT)
   < 3X upper limit of normal (ULN)

- Total bilirubin (TBL) < 2x ULN (unless Gilbert's disease or if liver involvement with lymphoma)

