#### 6.2.1.3 Dose Limiting Toxicities (DLTs)

The DLT window (ie, DLT evaluable period) will start on Day 1 (start of the administration of the first infusion). The duration of the DLT window is 28 days from infusion Day 1.

The DLT window may also be extended to assess events starting within the window in case the DLT definition is time dependent.

See Section 3.4 for description of DLT evaluability and replacement of subjects.

All available safety data for subjects who are not DLT evaluable will still be evaluated and considered in DLRT recommendations.

A DLT will be defined as any of the events described below occurring in a subject during the DLT window unless clearly attributable to causes other than AMG 562 treatment. The CTCAE version 4.0 (see Appendix A) will be used to assess toxicities/adverse

events with the exception of CRS and tumor lysis syndrome (TLS). See Section 6.2.1.4 and Appendix K for grading criteria of CRS, neurotoxicity and TLS respectively.

- 1. Death not clearly due to the underlying disease or extraneous causes.
- 2. Any subject meeting the criteria for Hy's Law case (ie, severe drug-induced liver injury [DILI]) will be considered a DLT. A Hy's Law case is defined as: AST or ALT values of ≥ 3x ULN AND with serum total bilirubin (TBIL) level of > 2x ULN or INR > 1.5 without signs of cholestasis and with no other clear alternative reason to explain the observed liver-related laboratory abnormalities (see Section 6.4 for hepatotoxicity management and Appendix A for further explanation of Hy's law case and Management of Hepatic Function)
- 3. Non-hematologic DLTs:
  - Non-hematological adverse event grade 3 or higher, EXCEPT:
    - infection responding to antibiotic/anti-infective treatment within 48 hours
    - grade 3 fatigue or asthenia
    - grade 3 headache that improves to grade ≤ 2 within 72 hours
    - grade 3 insomnia that improves to grade  $\leq$  2 within 72 hours
    - grade 3 fever that improves to grade  $\leq$  2 within 72 hours
    - grade 3 nausea, vomiting or diarrhea responding if managed with optimal medical support and resolves within 72 hours
    - laboratory parameters of grade ≥ 3, not considered clinically relevant , and improved to grade ≤ 2 within 72 hours
- 4. Hematologic DLTs:
  - Febrile neutropenia grade 3 or higher unless responding to antibiotic/anti-infective treatment within 48 hours
  - Grade 4 neutropenia lasting more than 5 days
  - Grade 4 thrombocytopenia lasting more than 7 days

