  - Grade 3 thrombocytopenia with hemorrhage or required platelet transfusion
  - Grade 3 anemia with symptoms or required intervention (eg, transfusion)
  - Grade 4 anemia in the absence of detectable lymphoma as it may reflect a marrow toxic effect of AMG 562

Any adverse event, that meets the DLT definition, occurring outside the DLT evaluation period that is determined by the investigator to be possibly related to AMG 562, which is seen more frequently or is more severe than expected or is persistent despite appropriate management, can be determined to be a DLT upon unanimous decision by the DLRT after review of the adverse event and all available safety data.

An event should be considered related to treatment if, in the investigator's medical judgement, there is a reasonable possibility that the event may have been caused by AMG 562.

The dosing schedule is described by Part 1 Study Design and Schema and also in the protocol synopsis.

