# Table 6. Infusion Interruptions/Delays/Withholding/Permanent Discontinuations and Management of Adverse Events Including Dose Reductions

	Interruption/ Delay	Specific Management	Re-start guidance	Permanent Discontinuation					
Infusion-related	ifusion-related Reaction (continued)								
Grade 3	Immediate interruption/ delay until event has improved to grade ≤ 1	Consider supportive therapy including steroids as clinically indicated. Increase monitoring of vital signs as medically indicated until the subject is deemed medically stable.	
 
As for grade 2 infusion-related reaction, with the exception of mandatory dose modification: reduce to next lower dose
 
	If subject missed more than 2 consecutive doses If recurrent grade 3					
Recurrent Grade 3 despite reduction of infusion rate & other measures	Immediate interruption	As for grade 3 infusion-related reaction	• n/a	Immediately stop the infusion (if applicable) and permanently discontinue AMG 562 therapy					
Grade 4	Immediate interruption	As for grade 3 infusion-related reaction	n/a	Immediately stop the infusion (if applicable) and permanently discontinue AMG 562 therapy					
Cytokine Releas	se Syndrome								
For Grading, Sto	or Grading, Stopping and Re-challenge Rules please refer to Table 7.								

Footnotes defined on last page of table

Page 2 of 5

Table 6. Infusion Interruptions/Delays/Withholding/Permanent Discontinuations and Management of Adverse Events Including
Dose Reductions

	Interruption/ Delay	Specific Management	Re-start guidance	Permanent Discontinuation
Any other adv	verse events including th	hose not meeting DL	.T criteria	
≥ Grade 3	Interruption/ delay required if deemed intolerable by the subject and not responding to appropriate medical management until event has improved to grade ≤ 1	n/a	
 
Re-start possible if successfully managed and improvement to ≤ grade 1 in ≤ 14 days.
 
In case of infusion interruption, continue treatment with next scheduled infusion, do not resume prior infusion or administer delayed infusion.
 
If next infusion is delayed:         
 
up to 72 hours: follow the schedule of assessments for the cycle day on which the infusion was originally planned. The following infusion should then be administered after 7 (± 1) days             

	If subject missed more than 2 consecutive doses In case of any event at grade 4

Footnotes defined on last page of table

Page 3 of 5

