- DLT (separate guidance for CRS, IRR and Neurotoxicity) or other unmanageable toxicity unless a subject has a clear clinical benefit from treatment, the toxicity has resolved to grade ≤ 1 or baseline and after consultation with the sponsor
- in case of grade 4 non-hematologic adverse event
- grade 3 neurotoxicity needing more than 7 days after treatment interruption to resolve to grade ≤1
- Grade 4 neurotoxicity
- Grade ≥ 3 seizure
- In case of occurrence of more than one seizure of grade ≤ 2
- treatment interruption: if the subject misses at least 2 consecutive doses due to serious adverse events/adverse events
- possible DILI requiring permanent withholding as per Section 6.4
- subjects who require more than 1 dose reduction
- clinically relevant disease progression
- relapse of disease subsequent to response on protocol treatment
- occurrence or progression of a medical condition which in the opinion of the investigator should preclude further participation of the subject in the study
- administration of relevant non-permitted concomitant medications
- requirement for alternative therapy
- subject's request
- subject or investigator not compliant with the study protocol

For grading of events, refer to Section 9.2.2.1.

Females who become pregnant while on study through 120 days after receiving the last dose of study drug will not receive subsequent scheduled doses and will be followed for safety until the EOS visit.

Males with pregnant partners or whose partners become pregnant while the subject is on study through 180 days after receiving the last dose of study drug must practice sexual abstinence or use a condom while on study through 180 days after receiving the last dose of study drug.

All reasons for treatment discontinuation should be clearly and comprehensively documented in the eCRF. If a subject has not continued to present for study visits, the investigator should determine the reason and circumstances as completely and accurately as possible.

In any case of premature treatment discontinuation, the investigator should make every effort to perform all examinations scheduled for the EOT.

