# 6.4.1 Criteria for Permanent Withholding of AMG 562 due to Potential Hepatotoxicity

AMG 562 should be permanently withheld and the subject should be followed according to the recommendations in Appendix A (Additional Safety Assessment Information) for possible DILI, if ALL of the criteria below are met:

• Increased AST or ALT from the relevant baseline value as specified below:

Baseline AST or A	LT value	AST or ALT elevation
< ULN		> 3 x ULN

AND

• TBIL > 2 x ULN or INR > 1.5

AND

- No other cause for the combination of the above laboratory abnormalities is immediately apparent; important alternative causes for elevated AST/ALT and/or elevated TBIL values include, but are not limited to:
  - hepatobilliary tract disease
  - viral hepatitis (eg, hepatitis A/B/C/D/E, Epstein-Barr virus, cytomegalovirus, herpes simplex virus, varicella, toxoplasmosis, and parvovirus)
  - right-sided heart failure, hypotension or any cause of hypoxia to the liver causing ischemia
  - exposure to hepatotoxic agents/drugs including herbal and dietary supplements, plants, and mushrooms,
  - heritable disorders causing impaired glucuronidation (eg, Gilbert's syndrome, Crigler-Najjar syndrome) and drugs that inhibit bilirubin glucuronidation (eg, indinavir, atazanavir)
  - alpha-one antitrypsin deficiency
  - alcoholic hepatitis
  - autoimmune hepatitis
  - Wilson's disease and hemochromatosis
  - nonalcoholic fatty liver disease including steatohepatitis (NASH)
  - non-hepatic causes (eg, rhabdomyolysis, hemolysis)

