# 6.4.2 Criteria for Conditional Withholding of AMG 562 due to Potential Hepatotoxicity

For subjects who do not meet the criteria for permanent discontinuation of AMG 562 outlined above and have no underlying liver disease and eligibility criteria requiring normal transaminases and TBIL at baseline or subjects with underlying liver disease and baseline abnormal transaminases, the following rules are recommended for withholding of Amgen investigational product and other protocol-required therapies:

Baseline AST or ALT value	AST or ALT elevation
Any	> 8x ULN at any time
Any	> 5x ULN but < 8x ULN for $\ge$ 2 weeks
Any	> 5x ULN but < 8x ULN and unable to adhere to enhanced monitoring schedule
Any	> 3x ULN with clinical signs or symptoms that are consistent with hepatitis (such as right upper quadrant pain/tenderness, fever, nausea, vomiting, jaundice.

• Elevation of either AST or ALT according to the following schedule:

- OR: TBIL > 3x ULN at any time
- OR: ALP > 8x ULN at any time

AMG 562 should be withheld pending investigation into alternative causes of the laboratory elevations. If AMG 562 is withheld, the subject should be followed according to recommendations in Appendix A for possible DILI. Rechallenge may be considered if an alternative cause for the elevated liver enzymes (ALT, AST, ALP) and/or elevated TBIL, is discovered and the laboratory abnormalities resolve to normal or baseline (Section 6.4.3).

Discontinuation of the product should be considered and the decision to rechallenge should be discussed with the Amgen Medical Monitor before reinitiating treatment with investigational product.

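### As printed, Section 6.4.1 cannot be met from a raised AST/ALT baseline, and after the DLT window one asymptomatic Hy's Law band is left with retesting and discretionary stopping only

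*Protocol*

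**What the plan says.** **Eligibility.** Inclusion 109 (Section 4.1) requires AST and ALT to be less than "3X upper limit of normal (ULN", so subjects may enter with raised transaminases.

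**Permanent withholding.** Section 6.4.1 requires every one of its criteria. The transaminase criterion is "Increased AST or ALT from the relevant baseline value as specified below", and the one printed row pairs a baseline below ULN with a rise above 3x ULN. The others are TBIL above 2x ULN or INR above 1.5, and no other cause immediately apparent.

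**Conditional withholding.** Section 6.4.2 gives recommended rules for subjects who do not meet 6.4.1. Its table applies to any baseline value: above 8x ULN; between 5x and 8x ULN for 2 weeks or more, or when enhanced monitoring cannot be kept; above 3x ULN with signs or symptoms of hepatitis, jaundice included. TBIL above 3x ULN or ALP above 8x ULN also triggers it. The lead-in describes subjects who "have no underlying liver disease and eligibility criteria requiring normal transaminases and TBIL at baseline", or who have underlying liver disease together with abnormal baseline transaminases.

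**DLT rule.** Section 6.2.1.3 says "Any subject meeting the criteria for Hy's Law case (ie, severe drug-induced liver injury [DILI]) will be considered a DLT". The definition has no baseline condition and excludes signs of cholestasis. The window is 28 days unless extended. Outside it, a qualifying event "can be determined to be a DLT upon unanimous decision by the DLRT".

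**Other routes.** Section 6.2.1.4.4 lists "possible DILI requiring permanent withholding as per Section 6.4", and Table 6 also refers hepatotoxicity to Section 6.4. The Table 6 row for other events of grade 3 or higher reads "delay required if deemed intolerable by the subject and not responding to appropriate medical management". Appendix A prescribes close observation: a repeat within 24 hours, then testing every 24 hours while TBIL is above 2x ULN or INR above 1.5.

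**The concern.** The protocol treats a Hy's Law case as severe drug-induced liver injury whatever the baseline, and SAP Section 9.6.3 summarises such cases without a baseline condition. After the DLT window, however, the same laboratory values with no other cause apparent lead to a permanent stop from a baseline below ULN. From a baseline at or above ULN they can lead to observation only. Nothing in the documents explains the difference.

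Section 3.5.1 anticipates a median treatment period of about 8 months, so most planned exposure lies after Day 28. Dosing is weekly, and Section 7.2.2 lets an infusion start before that day's predose laboratory results are available. Following the stated rules, dosing could continue while tests are repeated.

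There is a reporting consequence too. The automatic Appendix A report is tied to concurrent AST/ALT and TBL/INR elevation meeting the Section 6.4 criteria. Only 6.4.1 defines such a combination, so it is unclear whether the automatic report applies to these subjects.

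**Working it through.** There is no plan figure to reproduce; the check is an enumeration of the rules.

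**Inputs.** Thresholds from Sections 6.4.1, 6.4.2 and 6.2.1.3. Conditions assumed: baseline AST or ALT at or above ULN, no cholestasis (so the ALP trigger does not fire), no other cause apparent.

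**Grid.**
- AST/ALT states: above 3x to 5x ULN (1 state); above 5x and below 8x ULN, split by 2 weeks or more (yes/no) and monitoring possible (yes/no) (4 states); above 8x ULN (1 state). Total 1 + 4 + 1 = 6.
- TBIL (at most 2x; above 2x to 3x; above 3x ULN) by INR (at most 1.5; above 1.5): 3 x 2 = 6 cells. Dropping the one with neither TBIL above 2x nor INR above 1.5 leaves 5.
- Signs or symptoms: no or yes, 2.
- Patterns: 6 x 5 x 2 = 60, of which 30 are asymptomatic.

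**Results by rule.**

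| Rule | Patterns caught |
|---|---|
| 6.4.1, baseline below ULN | 60 of 60 |
| 6.4.1, baseline at or above ULN | 0 of 60 |
| 6.4.2, read as applying at any baseline | 54 of 60 |
| 6.2.1.3 Hy's Law DLT, within the window | 60 of 60 |

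**The 6 patterns missed by 6.4.2.** Two AST/ALT states (above 3x to 5x; above 5x and below 8x for under 2 weeks with monitoring kept) x three TBIL/INR cells (TBIL above 2x to 3x with INR at most 1.5; the same TBIL with INR above 1.5; TBIL at most 2x with INR above 1.5) x no symptoms = 2 x 3 x 1 = 6, which is 6 of the 30 asymptomatic patterns.

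**What applies to these 6 after the window.** Section 6.2.1.4.4 and Table 6 point back to 6.4. The general Table 6 row depends on the subject finding the event intolerable, which fits an asymptomatic laboratory finding poorly. A late DLT needs a unanimous decision. Appendix A orders tests, not a stop. What remains is judgement by the investigator or sponsor (Sections 6.2.1.4.4 and 8.2).

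**Infusions attributable to the gap.** Take Day 0 as the infusion at which the values are first drawn. It may be given before results at any baseline, so it is not attributable.
- Above 5x and below 8x ULN: Day 7 is attributable, and at Day 14 the 2-week row applies. One infusion.
- Above 3x to 5x ULN: no time limit, so one per week while the pattern lasts, or 28/7 = 4 in each 28 days after Day 0.

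**Two hypothetical cases after Day 28, no symptoms.**
- Case A: ALT from 1.5x to 4.5x ULN (4.5/1.5 = 3.0-fold), TBIL 2.5x ULN. In the band.
- Case B: ALT from 2.8x to 3.1x ULN (3.1/2.8 = 1.11-fold), INR above 1.5. Also in the band.

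**Boundary values.** Exactly 8x ULN falls between two 6.4.2 rows. Exactly 3x ULN meets 6.2.1.3 but not 6.4.1.

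**The case against.** **The table may be incomplete in the text reviewed.** Its header is split by extraction, and the phrase about a relevant baseline value suggests more than one row. A lost row cannot be excluded, so the 6.4.1 part is conditional on the source PDF. The 6.4.2 lead-in is running prose and does not depend on this.

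**The safeguards are substantial.** Every pattern in the band has TBIL above 2x ULN or INR above 1.5, so Appendix A always calls for retesting every 24 hours, and it adds a work-up of causes and consideration of a hepatology consult. A rise into a 6.4.2 trigger should be seen quickly. Section 9.1.3 names drug-induced liver injury as an example of a medically important serious event, so reporting on judgement remains. Section 6.2.1.4.4 also discontinues for unmanageable toxicity, though whether an asymptomatic laboratory picture qualifies is again judgement. All of this stands and limits the consequence; none of it is a withholding rule.

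**Conditional handling of raised baselines is defensible.** Case B shows why: a 1.1-fold rise should not automatically end treatment in relapsed or refractory lymphoma. A reader might infer that a permanent stop above 3x ULN is needed for everyone. The documents do not support that; they support at least withholding while the cause is sought.

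**The contrast should not be overdrawn.** A reader might infer that raised-baseline subjects have no liver rule, or that this band alone lacks a binding one. Neither holds. The 6.4.2 table covers any baseline, and its rules are recommendations for every pattern they catch. Even within the window, discontinuation for a DLT has an exception: clear clinical benefit, resolved toxicity and sponsor consultation.

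**Liver involvement by lymphoma.** Inclusion 109 waives the TBL limit "unless Gilbert's disease or if liver involvement with lymphoma", and the 6.4.1 list of causes does not name involvement by lymphoma. That list is expressly not exhaustive, so no change is needed there.

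**Conclusion.** The point holds for the plan as printed, in a narrow form, and is best labelled a cheap improvement. A subject with baseline AST/ALT at or above ULN cannot meet 6.4.1, and 6 of 60 Hy's Law rule patterns also escape 6.4.2. After the DLT window those 6 have daily retesting and discretionary stopping only.

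Separately, the 6.4.2 lead-in refers to an eligibility requirement for normal transaminases that this protocol does not have. Read literally, it omits raised-baseline subjects without underlying liver disease. A reader might infer that 6.4.2 does not protect them at all. The any-baseline rows point the other way, and the count of 54 rests on that reading.

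The conclusion assumes that no table row was lost, no cholestasis, no listed sign or symptom, monitoring kept and no other cause apparent. The documents give no rate for raised baselines or for reaching this band, so no number of affected subjects is claimed. No statistical figure changes. The SAP records that the study was discontinued with one subject ongoing, so the point concerns the plan as written and any reuse of its text.

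**What to change.** First check the 6.4.1 table in the source PDF. If no row is missing:

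1. State in Section 6.4 that any case meeting the 6.2.1.3 Hy's Law definition, with no other cause apparent, requires AMG 562 to be withheld pending work-up under 6.4.2, whatever the baseline or study day.
2. Reword the 6.4.2 lead-in to cover all eligible subjects. This is worth doing even if a table row turns out to have been lost.
3. Tie the Appendix A reporting trigger to the same Hy's Law definition.

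Whether a raised-baseline case then stops permanently, and at what multiple of baseline, is a clinical trade-off for the sponsor's hepatic experts; Cases A and B show the range they would need to separate.

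The cost is a few lines in an amendment and no new tests. The downside is a few more subjects temporarily withheld, including some whose entry values were already raised.

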# 6.4.2 Criteria for Conditional Withholding of AMG 562 due to Potential Hepatotoxicity

For subjects who do not meet the criteria for permanent discontinuation of AMG 562 outlined above and have no underlying liver disease and eligibility criteria requiring normal transaminases and TBIL at baseline or subjects with underlying liver disease and baseline abnormal transaminases, the following rules are recommended for withholding of Amgen investigational product and other protocol-required therapies:

Baseline AST or ALT value	AST or ALT elevation
Any	> 8x ULN at any time
Any	> 5x ULN but < 8x ULN for $\ge$ 2 weeks
Any	> 5x ULN but < 8x ULN and unable to adhere to enhanced monitoring schedule
Any	> 3x ULN with clinical signs or symptoms that are consistent with hepatitis (such as right upper quadrant pain/tenderness, fever, nausea, vomiting, jaundice.

• Elevation of either AST or ALT according to the following schedule:

- OR: TBIL > 3x ULN at any time
- OR: ALP > 8x ULN at any time

AMG 562 should be withheld pending investigation into alternative causes of the laboratory elevations. If AMG 562 is withheld, the subject should be followed according to recommendations in Appendix A for possible DILI. Rechallenge may be considered if an alternative cause for the elevated liver enzymes (ALT, AST, ALP) and/or elevated TBIL, is discovered and the laboratory abnormalities resolve to normal or baseline (Section 6.4.3).

Discontinuation of the product should be considered and the decision to rechallenge should be discussed with the Amgen Medical Monitor before reinitiating treatment with investigational product.

